### Methods: Data collection, management, and analysis

Data collection methods 17a Administrative data will be provided to the research team by the AHS data analytics team in either anonymous format (for diagnosed concussions where a parent did not use the web portal or chose to do so anonymously) or a format where personal identifiers are stripped after linkage (for parents who used the web portal and provided consent for linkage). To log in to the web portal, parents and children will provide an email address, password, and the child's name to create an account. This information will not be retained by the study team and investigators will not have access to that information. The web portal may also be used anonymously. Web portal content will be targeted to specific age cohorts:  
1) primary pathway for youth age 6-13; 2) secondary pathway for adolescents age 14-17; and 3) caregiver pathway for parents/guardians. Thus, age of the child is required when accessing the web portal.

To determine whether the implementation of the CP leads to changes in healthcare utilization (e.g., greater use of outpatient care and less reliance on care in emergency departments), and whether such changes are linked to better child outcomes, healthcare numbers will be obtained by willing families. Once data collection is completed, the research coordinator will destroy any identifying information.

The Health and Behaviour Inventory (HBI) and Pediatric Quality of Life (PedsQL) questionnaires will be voluntarily completed by families through the web portal. No data will be entered by the study team. The HBI is a 20-item scale commonly used to assess the frequency of cognitive and somatic pediatric concussion symptoms on a Likert scale of 0 (never) to 3 (often). The PedsQL is a valid and reliable, 23-item model designed to measure the core dimensions of health as delineated by the World Health Organization, as well as role (school) functioning. 4 scales (physical, emotional, school and social functioning) are used to measure health-related quality of life in healthy children and adolescents and those with acute and chronic health conditions.

17b The web portal will send email reminders to participating families to complete serial symptom inventories. No contact will be made by the study team unless families reach out voluntarily. Ideally, symptom data will be collected until participants fully recover, however, participants can stop entering data, or leave the study at any time.

Data management 18 The study team will not directly access AHS databases or systems. Administrative data will be accessed externally by an AHS MyChild analyst. The variables collected will be obtained for all children diagnosed with concussion at any of the participating AHS facilities during the conduct of the stepped wedge clinical trial. The data will be de-identified, except for children whose parents have consented to linkage of web portal responses with health records. Individual data entered through the web portal by parents and children will download into the secure REDCap database. The database servers will be located under Canadian jurisdiction and be administered by the Clinical Research Unit of the University of Calgary. These servers are part of the CRU infrastructure and maintained in accordance with strict security and privacy controls.

Results from the project will be reported in aggregate format. If individual materials are presented, all personal identifiers will be removed. These safeguards should maintain confidentiality and minimize any risks associated with participation in the project.

Statistical methods 19a Statistical analyses will involve comparisons of primary and secondary outcomes prior to versus after CP implementation. Children will fall into either the pre-CP or post-CP group because their care (including the version of the website and text messaging they receive) will be based strictly on when they present for acute care (i.e., prior to or after CP implementation at their respective site). Time to symptom resolution will be the primary outcome, and will be examined using survival analyses. First, Kaplan Meier estimates of the curves will be created, to obtain crude comparisons; Cox proportional hazards models will then be used to adjust for other variables. Apart from reporting hazard ratios, we also will present median time to symptom resolution (if reached) for pre- versus post-CP implementation. Other outcomes will be examined using mixed models with random effects for cluster, to adjust for clustering by site, and fixed effects for the test of CP status (pre/post implementation). Linear models will be used for continuous outcomes, Poisson for counts, and logistic regression models for binary outcomes. Exploratory analyses will examine whether the impact of implementation changes as sites gain more experience with the CP, by including the amount of time since the CP was implemented as a fixed effect in the model. Similarly, heterogeneity in intervention effects will be explored using testing interactions of CP status (pre/post) with site.

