As shown in Table 3 on the next page, we have planned a comprehensive evaluation of both process and clinical outcomes to fulfill our second objective. Clinical outcomes will include four patient-centered outcomes, and process outcomes will include five measures of adherence to the CP (e.g., physician provision of discharge instructions; patient/parent adherence to key interventions as recommended by the CP). Physicians and nurses in the ED will distribute a concussion handout at discharge. The front page will advise the family to go to the RECOVER web portal for more information, and the last 4 pages will provide concussion education and advice, including about return to learn and return to play. Prior to CP implementation, the website will provide parents with tools to help track recovery; after CP implementation, it will also supply evidence-based information about how to promote recovery and obtain appropriate concussion care. Both prior to and after CP implementation, the website interface will ask patients and parents to rate their satisfaction with their care in the ED within 3 days of their visit, as well as their comprehension of and adherence to physician discharge recommendations, including those regarding return to school and return to play. They also will report on whether they perceive the patient to have returned to pre-injury status, and provide ratings of the patient's post-concussive symptoms and quality of life. Parents and patients will be blinded to site allocation. They will be able to provide their responses anonymously, or they can elect to provide informed consent to enable us to link their responses on the website to identifying information and medical data.

12b The primary outcome will be the time to symptom resolution based on weekly reports of whether the patient has returned to pre-injury status. Secondary patient-centered outcomes will include ratings of satisfaction with ED care and post-injury ratings of post-concussive symptoms and quality of life. The latter two outcomes will be assessed using the Health and Behaviour Inventory and the PedsQL, both of which are measures included in the NIH Common Data Elements for pediatric traumatic brain injury (see Surveys and Questionnaires in appendices).

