Secondary outcomes also will include measures of physician adherence, the number of unique website hits per IP address, the proportion of patient- and parent-reported adherence to physician discharge recommendations, the proportion of diagnosed concussions per visit (predicted to increase as physicians identify and code the injuries correctly), and the proportion of CT scans ordered per diagnosed concussion (predicted to decrease because the CP will include prediction rules for CT scanning in concussion).

12c *Table 3: Process and clinical outcomes*

| Outcome measure      | Description         | Details  |
|-----------------------------|----------------------------|---|
| Primary clinical outcome    | Time to symptom resolution | Weekly ratings by patients and parents of whether patient has returned to pre-injury status   |
| Secondary clinical outcomes | Postconcussive symptoms    | Weekly ratings on Health and Behaviour Inventory  |
|                             | Quality of life            | Weekly ratings on PedsQL  |
|                             | Satisfaction with care     | Post-visit rating of overall satisfaction with acute care   |
| Primary process outcome     | Physician adherence        | Proportion of completed discharge forms per diagnosed concussion    |
| Secondary process outcomes  | Patient/parent adherence   | Proportion of patient and parent reports of adherence to physician discharge recommendations involving rest, return to school, and return to play |
|                             | Patient/parent adherence   | Number of unique website hits per IP address  |
|                             | Physician adherence        | Proportion of diagnosed concussions per visit   |
|                             | Physician adherence        | Proportion of CT scans ordered per diagnosed concussion   |

Qualitative interviews and site surveys resulted in the discharge form being replaced by the 5P risk score sticker. To assess adherence, the study team recorded the number of 5P assessments completed by each site over the course of data collection.

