*Power calculation.* Power calculations for the primary outcome, time to symptom resolution, were computed using standard methods for two-group survival analyses (i.e., children who received care before versus after implementation of the CP). We conservatively assumed a sample size of 1,575, based on a total of 2,100 concussions per year across sites, a 50% rate of web site usage, and 18 months of recruitment. If we assume equal numbers of cases in the pre- and post-implementation phases, a median time to symptom resolution of 4 weeks, non-informative censoring because follow up will continue for 3 months, and no clustering effects, then the minimum hazard ratio that we can detect with .80 power at a significance level of .05 would be 1.20, which would represent at 20% higher likelihood of symptom resolution at any given time post-injury after implementation of the CP. Analyses will treat the randomised crossover from control to intervention as having occurred at the planned time, irrespective of any delays in actual implementation of the intervention, although secondary analyses will explore the effects of the actual timing of the crossover should any delays occur. All sites have provided written commitment to the study. Therefore, barring exceptional circumstances, no sites will be lost to follow-up.

Randomization

15

A study statistician will use a computerized algorithm to select a randomly generated order of implementation for the four sites.

Recruitment 16 Recruitment will rely on ongoing support and communication with clinicians. To avoid having implementation become stalled or displaced by other priorities, we will conduct monthly teleconferences with site champions to discuss progress and sustainability. Teleconferences will allow sites to discuss best practices and local solutions to common barriers. Additionally, the study coordinator and PI will be available for more informal consultation by email or phone.

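### Item 17b aims to collect symptom ratings only as far as full recovery, so later weekly HBI (and by inference PedsQL) comparisons are selected on the primary outcome and are likely to dilute a benefit of the pathway

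*Protocol*

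**What the plan says.** Item 17b describes the end of data entry in one sentence. It opens "Ideally, symptom data will be collected until participants fully recover" and goes on to let families stop or withdraw whenever they wish. Just before it, the same item says: "The web portal will send email reminders to participating families to complete serial symptom inventories". Item 17a adds that the HBI and PedsQL "questionnaires will be voluntarily completed by families through the web portal".

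Table 3 (item 12c) lists both instruments as secondary clinical outcomes, as "Weekly ratings on Health and Behaviour Inventory" and "Weekly ratings on PedsQL". It gives neither a last week nor an analysis week. Item 12b confirms their role: "Secondary patient-centered outcomes will include ratings of satisfaction with ED care and post-injury ratings of post-concussive symptoms and quality of life". The primary outcome in item 12b is time to symptom resolution, taken from weekly reports of whether the child is back to pre-injury status.

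Item 19a analyses the non-survival outcomes with mixed models that have a random effect for site and a fixed effect for pre/post status. It does not mention ratings that end at recovery. The power calculation in item 14 assumes "non-informative censoring because follow up will continue for 3 months".

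**The concern.** The primary event determines who still supplies the secondary outcomes. Even in the best case that item 17b describes, a child's symptom series runs to recovery, and the rest of the sentence only allows it to end sooner. From the first recoveries onward, each week's raters are increasingly those who have not recovered.

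If the CP works, the two phases lose children at different rates. More post-CP children leave, and those left behind are that phase's slower recoverers. A faster recovery then shows up partly as good scores that were never recorded, so the later pre/post contrast is made between groups selected by outcome.

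HBI and PedsQL are the trial's two graded measures of the better health outcomes sought in objective 2. Because this is a matter of data collection, an analysis plan could only model scores that do not exist.

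**Working it through.** **Inputs.** From item 14: median time to resolution 4 weeks, hazard ratio 1.20, N = 1,575, equal numbers pre and post, 3 months of follow-up. From item 17a: the HBI has 20 items scored 0 to 3, so its range is 0 to 60. Assumed: exponential time to recovery, and no drop-out before recovery.

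**The plan's own figures.** 2,100 × 0.50 × 1.5 years = 1,575, which reproduces. The hazard ratio of 1.20 does not reproduce as the minimum detectable at 0.80 power. At 12 weeks, events = 1,575 × (0.875 + 0.918)/2 ≈ 1,412, and exp[2(1.96 + 0.842)/√1,412] ≈ 1.16. That is a separate matter. Here 1.20 serves only as the protocol's stated effect.

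**Share still unrecovered at week w.** Pre-CP: 0.5^(w/4). Post-CP: 0.5^(1.2w/4). Counts use 1,575/2 = 787.5 children per phase and are upper limits, since families may stop earlier.

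| Week | Pre-CP | Post-CP | Children, pre v post |
|---|---|---|---|
| 4 | 0.500 | 0.435 | 394 v 343 |
| 8 | 0.250 | 0.189 | 197 v 149 |
| 12 | 0.125 | 0.082 | 98 v 65 |

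By week 12, ratings that ended at recovery would have lost about 87% of pre-CP and 92% of post-CP children. The remaining post-CP share is about two thirds of the pre-CP share (0.082/0.125 = 0.66).

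**Effect on the HBI contrast.** The protocol gives no HBI distribution, so two illustrative simulations bracket it. Differences are post minus pre; negative means benefit.

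*Model A.* HBI is 20 at injury and decays exponentially. Recovery is a score below 4, with median 4 weeks. The CP speeds decay by 20%, and the log-SD of the decay rate is 0.6 to 0.9. The rating at which recovery is first seen is kept.

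| | All children | Children still rating |
|---|---|---|
| Week 2 | −1.01 to −1.17 | −0.83 to −1.09 |
| Week 4 | −0.85 to −0.96 | −0.48 to −0.55 |
| Week 8 | about −0.5 | −0.24 to −0.30 |
| Weeks 1–12 pooled | −0.66 to −0.68 | −0.41 to −0.42 |

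Nothing is lost at week 1 and about 7% to 19% at week 2. At week 4 the loss is just over 40% (1 − 0.48/0.85 = 44%; 1 − 0.55/0.96 = 43%).

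*Model B.* Mean HBI is 15 while unrecovered and 4 once recovered, with severity SD 5. The link between severity and slow recovery runs from none to strong, and the score of unrecovered children either stays level or falls by 0.5 a week. Pooled over weeks 1–12:

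- all children rated: −0.36 to −0.61
- stopping at recovery, recovery rating kept: −0.30 to +0.03
- unrecovered ratings only: +0.01 to +0.31

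The pooled benefit shrinks in every scenario of both models. In Model B it also vanishes or reverses in many. The direction is consistent; the size is not fixed.

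**The case against.** The strongest reply is that item 17b contains no stopping rule. The sentence is an aspiration about retention, set against earlier drop-out. Nothing says that the portal closes, that reminders cease or that a recovered child may not rate. A reader might infer that later ratings come only from unrecovered children; the text does not go that far, because some recovered families may carry on. What remains is that no section asks them to, and those who do so are self-selected.

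Other points on that side also stand:

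- **PedsQL.** Item 17b speaks of symptom data and symptom inventories. Extending it to PedsQL is an inference from the shared portal and weekly schedule.
- **Three months.** A reader might see a contradiction with item 14. There is none for the primary outcome, since following a child to recovery or 3 months is ordinary survival follow-up. The two items are merely not aligned: one gives 3 months and the other no maximum.
- **Relapse.** A reader might add that returning symptoms would go unseen. Nothing says that a single report of recovery ends collection, so this is not supported.
- **Size.** The points lost at week 4 in Model A are about 0.4 on a 60-point scale, and every HBI parameter is assumed.

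A further reply is that the analysis week, repeated-measures structure and missing-data method may sit in a statistical analysis plan that is not at hand. If the recovery rating is recorded, a participant-level model could remove part of the bias. That is fair, but if no child were rated after recovery, such a model would rest on assumptions the data could not test.

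**Conclusion.** The point holds in a limited form. Followed as written, item 17b lets the primary event decide who supplies later HBI ratings, and by inference later PedsQL ratings. The pre/post comparison of those ratings is then selected on outcome and likely to understate a CP benefit.

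The unrecovered shares in the first table rest on the protocol's median and hazard ratio plus an exponential curve. The loss in HBI points rests on assumed score distributions and on whether the recovery rating is kept. With it kept, week 1 is unaffected and week 2 only slightly. A reader might conclude that the design hides a benefit altogether. That is too strong: Model A keeps the sign throughout, and only some scenarios of Model B lose it.

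The primary time-to-event analysis is not touched by this point. It concerns secondary outcomes, but scores not collected cannot be recovered later, so it is worth settling in the protocol.

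**What to change.** In item 17b, state that automated portal prompts for HBI and PedsQL go to every child in both phases at fixed weeks up to week 12 after the emergency visit (for example weeks 4, 8 and 12), whether or not recovery has been reported. Compare HBI and PedsQL at those weeks among all children, recovered ones included. Align Table 3, item 14 and item 17b on when follow-up ends.

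This takes a short addition to the text and a change to the automated email schedule; it needs no staff contact. Recovered families receive a few more questionnaires. Some non-response will remain because completion is voluntary, so the change reduces selection by recovery but does not abolish it.

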Health care utilization and costs associated with care of concussion will be compared before and after the implementation of the CP. Utilization and costs are expected to remain stable or decline following implementation of the CP.

*Overview.* The project will involve a stepped wedge cluster randomised trial to evaluate the implementation of the MNCY CP for the acute care of pediatric concussion. Stepped wedge designs randomise the sequence in which participating sites receive the study intervention, so that each site serves as its own control, but each site starts the intervention at a different time. Data collection continues throughout, so that each site contributes observations during both pre-intervention and post-intervention periods. In this case, each of four participating sites will be considered clusters, and they will be randomised to implement the MNCY CP over 11 months (i.e., after a 2 month lead-in period, implementation will occur at one site and then at the other three sites every 2 months, until implementation has occurred at all four sites, with data continuing to be collected 2 months after the CP is implemented at all sites).

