- 9 The four sites, each of which will be treated as a cluster in the analysis, are Alberta Children's Hospital and South Health Campus in Calgary (treated as a single site because they are staffed by the same group of pediatric physicians), and Stollery Children's Hospital, North East Community Health Center, and Grey Nun's Hospital in Edmonton (each of these Edmonton sites is staffed by different physician groups and will therefore be treated separately). The sites were selected because they represent high-volume centres that account for a significant proportion of children diagnosed with concussion in acute care settings in Alberta. Collectively, they accounted for 2,098 concussion diagnoses over 12 months in 2015-2016, as well as another 1,517 cases with the diagnosis of head injury, unspecified, which is often used in place of the more specific diagnostic code (see Table 1 on next page). Our project team includes the emergency medicine physicians who are the academic and clinical leaders for emergency medicine in both Calgary ([name]) and Edmonton ([name]).

All four clinical sites have provided enthusiastic letters of support for the proposed project, and will allocate staff time and provide space for project activities as in-kind contributions. More specifically, the operational leads at the sites have agreed to encourage the participation of their physicians and nurses in the project and to provide space needed for project site visits, key informant interviews, and staff training. The participation of the PI, Co-PIs, and all Co-Investigators is strongly supported by their respective academic institutions.

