12d *Health care utilization.* We will assess the impact of the implementation of the CP on health care utilization using data from the National Ambulatory Care Reporting System (NACRS). Relevant outcomes will include acute care length of stay and return visits within 72 hours following acute care discharge. Appropriate procedures will be used to link administrative and health data. Use of NACRS data allows efficient capture of return visits, regardless of whether the patient returns to the index site. We will also use administrative data from AHS to assess health care utilization for pediatric patients with concussion. For each concussion diagnosed at the target sites, we will track the duration of stay in the ED, number of subsequent outpatient visits, and number of referrals to other health care services.

*Healthcare costs.* Payer costs associated with acute care for pediatric patients with concussion will be accounted for, based on ED visits, return visits, and physician fees, as well as subsequent outpatient care, which will be determined from the AHS administrative database. Costs for ED visits will be based on standard methodologies using resource intensity weightings (RIWs). Physician fees associated with ED and outpatient visits, including those for laboratory and diagnostic imaging services, will be captured through associated AHS billings. Cost data will be presented in Canadian dollars for the standard price year of 2014.

Participant timeline 13a *Project phases.* As shown in the Project Timeline below, the project will be divided into four phases. During the pre-implementation phase, which will last 12 months, we will complete site visits and key informant interviews, develop the intervention strategy, seek site approvals for the planned intervention, conduct a launch meeting, and complete randomization. The implementation phase will take place over the next 10 months. According to the stepped wedge design, data collection will occur continuously from 2 months prior to implementation at any site until 2 months after the CP is implemented at all four sites. Data collection will include the monitoring of outcomes, which are described below, during the course of the stepped wedge trial, which will last about 10 months.

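### Item 19a names no site term for the primary Cox model, although the protocol says sites are clusters in the analysis and gives every other outcome a cluster effect

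*Protocol*

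**What the plan says.** Item 9 (study setting) makes a general statement: "The four sites, each of which will be treated as a cluster in the analysis". The Overview of the design also calls the sites clusters.

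Item 19a (statistical methods) treats the outcomes differently. The primary outcome gets crude Kaplan-Meier curves, after which "Cox proportional hazards models will then be used to adjust for other variables". No covariate is listed, and no site effect, stratum, frailty or cluster-robust variance is named. The next model sentence reads: "Other outcomes will be examined using mixed models with random effects for cluster, to adjust for clustering by site". Site otherwise appears in 19a only in defining pre/post status and in exploratory work.

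Item 14 computes power for the primary outcome as a two-group survival comparison that assumes "non-informative censoring because follow up will continue for 3 months, and no clustering effects".

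Three durations are given. The Overview says of the sites that "they will be randomised to implement the MNCY CP over 11 months", with these steps: "after a 2 month lead-in period, implementation will occur at one site and then at the other three sites every 2 months". Item 13a collects data "during the course of the stepped wedge trial, which will last about 10 months". Item 14 takes its sample size "based on a total of 2,100 concussions per year across sites, a 50% rate of web site usage, and 18 months of recruitment".

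**The concern.** A stepped wedge lets each site act as its own control. A Cox model that pools sites gives that up. Sites that cross over early contribute mostly post-implementation children, and sites that cross over late contribute mostly pre-implementation children. Any difference in recovery between sites then enters the pre/post hazard ratio.

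Since the order is random, this does not bias the estimate on average over orders. But the trial realises one order of only four sites, and the pooled standard error takes no account of that chance element. The confidence interval for the primary outcome would be too narrow and the test would reject too often. Site differences are plausible here: item 9 describes tertiary children's hospitals and community sites, staffed by different physician groups.

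**Working it through.** **The plan's own figures.** N = 2,100 × 0.5 × 18/12 = 1,575, as stated. With a 4-week median and 3 months of follow-up taken as 13 weeks, the event probability is 1 − 2^(−13/4) = 0.895, which gives 1,409 events. With a 1:1 split, the detectable hazard ratio (80% power, two-sided 5%) is exp(2.80 × 2/√1,409) = 1.16, not 1.20. A ratio of 1.20 needs about 945 events, or 60% of 1,575. So at its own N the stated 1.20 is conservative before site is considered.

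**Inputs for the site check.**
- Steps at months 2, 4, 6 and 8 (Overview).
- Duration T of 10 months (item 13a, and the sum of the Overview's steps), 11 months (Overview) or 18 months (item 14).
- N = 2,100 × 0.5 × T/12 = 875, 962 or 1,575. Events at 0.895 = 783, 861 or 1,409.
- Assumed, because the documents do not give them: four equal sites (w = 1/4), and a between-site SD of the log hazard of 0.05, 0.10 or 0.20.

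**Formulas.** The post-implementation share at a site is p = (T − step)/T, with mean P.
- Pooled SE = 1/√(events × P(1−P)).
- Site differences add a standard deviation of m × SD to the pooled log hazard ratio, with m = √(Σw²(p−P)²)/(P(1−P)).
- Type I error = 2[1 − Φ(1.96 × SE/√(SE² + (m × SD)²))].
- Share of information kept with a site term = mean p(1−p)/(P(1−P)).
- Power at 1.20 = Φ(ln 1.20/SE − 1.96). Detectable ratio = exp(2.80 × SE).

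| | 10 months, N=875 | 11 months, N=962 | 18 months, N=1,575 |
|---|---|---|---|
| Post share by site (%) | 80/60/40/20 | 82/64/45/27 | 89/78/67/56 |
| P | 0.500 | 0.545 | 0.722 |
| Pooled SE | 0.0715 | 0.0684 | 0.0595 |
| m | 0.447 | 0.410 | 0.310 |
| Type I error, pooled, SD 0.05/0.10/0.20 (%) | 6.1/9.7/22.1 | 6.0/9.3/20.9 | 5.8/8.2/17.5 |
| Information kept with site (%) | 80 | 83 | 92 |
| SE with site | 0.0799 | 0.0750 | 0.0619 |
| Power at 1.20, pooled to with site (%) | 72 to 63 | 76 to 68 | 87 to 84 |
| Detectable ratio, pooled to with site | 1.22 to 1.25 | 1.21 to 1.23 | 1.18 to 1.19 |

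Example, 10 months and SD 0.10: m × SD = 0.0447; √(0.0715² + 0.0447²) = 0.0843; 1.96 × 0.0715/0.0843 = 1.66; two-sided tail 9.7%.

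**Simulation** (3,000 trials per setting, exponential times, censoring at 13 weeks, no calendar trend). Pooled type I error at SD 0.05/0.10/0.20 is 6/10/22%, 6/9/20% and 6/8/17% for the three schedules. Stratified by site it is about 4 to 5% in every setting.

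**Item 14's N and equal split kept together.** With N=1,575 and shares of 80/60/40/20%, pooled type I error is 7/13/32%. Power at 1.20 goes from 93% to 86% with site, and the detectable ratio from 1.16 to 1.18.

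**The case against.** **This belongs in the SAP.** Item 9 covers the whole analysis without exception, the unlisted variables could include site, and the exploratory site interactions would normally bring a site main effect. It is true that 19a does not exclude site, and the pooled model is the least favourable reading. But 19a itself fixes the cluster term for every outcome except the primary one, and item 14 assumes no clustering for that same outcome. The text as written permits the pooled model.

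**Sites are not equal.** Item 9 gives annual ED volumes of over 77,000 plus 15,000 for the combined Calgary site, about 50,000 for one Edmonton site, and about 18,000 for the other two together. Using ED volume as a proxy for concussions and splitting the 18,000 evenly, the shares are about 58/31/6/6%. Over all 24 orders at 10 months and N=875, pooled type I error ranges over 5–8%, 6–16% and 11–38% at the three SDs. Information kept ranges from 69 to 93%, and power with site from 55 to 69%. This stands: the result depends on the realised order. The averages over orders, about 6, 10 and 21%, hardly move.

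**The 18-month case is artificial.** Steps at months 2 to 8 within 18 months put 72% of children after implementation, against item 14's equal split and the Overview's end of data collection. That is so, and it is why item 14's own N and split are also shown. With the unequal shares, the 18-month detectable ratio with site is 1.17 to 1.22, so reaching that N does not guarantee 1.20.

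**Stratifying does not settle everything.** The simulated 4 to 5% assumes no calendar trend, and pathway status is correlated with calendar time in a stepped wedge. This also stands; a site term does not deal with it.

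**Conclusion.** The concern holds. Item 19a leaves open whether the primary analysis treats site as a cluster, against the general statement in item 9. If the model is pooled, the defect is understated uncertainty, not average bias. Its size depends on a between-site SD that the documents do not give: none if sites do not differ, about one percentage point at 0.05, and a type I error of 17 to 22% at 0.20 across the three schedules with equal sites (up to 32% with item 14's N and equal split).

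The stated detectable ratio of 1.20 is not met at the 10- or 11-month N, even without a site term. With site it exceeds 1.20 in every order at those sample sizes, also under the unequal site shares. At item 14's N and equal split it survives the site term (1.18 with equal sites).

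That 19a names no site adjustment for the primary outcome is clear from the text. The size of the effect is less certain.

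**What to change.** In item 19a, state that the primary Cox model for pathway status is stratified by site, or has fixed site effects. Either suits four clusters better than a frailty or a cluster-robust variance, which are unreliable with so few. Keep the Kaplan-Meier curves as crude comparisons.

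In item 14, recompute the detectable hazard ratio with site in the model, and with an N that matches one recruitment period reconciled across the Overview, item 13a and item 14.

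The change is one line in 19a and one recalculation. It needs no new data, since site is already required to assign pre/post status. The price is the loss of information tabulated above, 8 to 20% with equal sites. Adjustment for calendar time is a separate decision.
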